2.4.4.3 Multiplicity issues

The multiplicity procedure is proposed to control the overall type-I error rate for testing the co-primary and selected secondary endpoints. The overall alpha is 0.05. The comparisons with placebo will be tested based on the hierarchical order below at 2-sided $\alpha = 0.05$:

1) Co-primary efficacy endpoints:

In countries other than Japan:

- Change from baseline in NC and in NPS at Week 24 for 300mg q2w versus placebo.

[figure not shown]
In Japan:

- Change from baseline in NC, in NPS, and in CT LMK at Week 24 for 300mg q2w versus placebo.

2) Secondary efficacy endpoints:

- Change from baseline in CT LMK score at Week 24 for 300mg q2w versus placebo (this will not be a secondary endpoint for Japan as it is already a co-primary endpoint).
- Change from baseline in TSS at Week 24 for 300mg q2w versus placebo.
- Change from baseline in UPSIT at Week 24 for 300mg q2w versus placebo.
- Change from baseline in loss of smell daily symptoms at Week 24 for 300mg q2w versus placebo.
- Change from baseline in SNOT-22 at Week 24 for 300mg q2w versus placebo.
- Change from baseline in NPS at Week 52 for q2w (Arm A) versus placebo (Arm C).
- Change from baseline in NC at Week 52 for q2w (Arm A) versus placebo (Arm C).
- Change from baseline in SNOT-22 at Week 52 for q2w (Arm A) versus placebo (Arm C).
- Proportion of patients requiring rescue treatment defined as: use SCS or NP surgery (actual or planned) during the treatment period for 300mg q2w versus placebo using the pooled data from the EFC14280 and EFC14146.[†]
- Change from baseline in FEV1(L) at Week 24 for 300mg q2w versus placebo for patients with co-morbid asthma using the pooled data from the EFC14280 and EFC14146.*

The figure below shows hierarchies for individual studies of EFC14280 and EFC14146 as well as the pre-specified pooled analysis for proportion of patients requiring rescue treatment with SCS or NP surgery and change from baseline in FEV1(L) at Week 24.

†: The pooled analysis for this endpoint (Proportion of patients requiring rescue treatment with SCS or NP surgery) will be tested in the hierarchy only when in both EFC14280 and EFC14146 hierarchies, all endpoints before this one reach statistical significance with p -value ≤ 0.05 .

*: The pooled analysis for this endpoint (Change from baseline in FEV1 at Week 24) will be tested in the hierarchy only when the previous endpoint (the pooled analysis for the proportion of patients requiring rescue treatment with SCS or NP surgery) achieves statistical significance in this hierarchical testing procedure as described in the previous paragraph.

In countries other than Japan, the study is considered positive when both co-primary endpoints, the change from baseline in NC and in NPS at Week 24, achieve statistical significance.

In Japan, the study is considered positive when all co-primary endpoints, the change from baseline in NC, in NPS, and in CT LMK at Week 24, achieve statistical significance.

2.4.4.4 Additional efficacy analyses

2.4.4.4.1 Comparisons for other secondary efficacy endpoints

- Comparisons at Week 24 will be made between pooled arms A and B versus placebo.
- Comparisons at Week 52 will be made between Arm A versus placebo
- Comparisons will be made for the following secondary endpoints:
 - Change from baseline and time course profiles in NPS, NC, LMK, TSS, UPSIT, daily assessed loss of smell, SNOT-22 at Week 52,
 - Change from baseline at Week 24 in NPIF,
 - Change from baseline at Week 24 and Week 52 in:
 - VAS for overall rhinosinusitis,
 - VAS for EQ-5D
 - In the severity of rhinorrhea (anterior/posterior nasal discharge) daily symptom score assessed by the patient,
 - Percent change from baseline at Week 24 and Week 52 and time course profiles in:
 - NC,
 - daily assessed loss of smell,
 - TSS,
 - Percent change from baseline at Week 24 and Week 52 in VAS for overall rhinosinusitis
 - Proportion of responders at Week 24 (defined as patients with improvement by at least 1 point in NPS),
 - Proportion of responders at Week 24 (defined as patients with improvement by at least 2 points in NPS),
 - Proportion of patients with improvement by at least 1 point in NPS and 0.5 reductions in NC at Week 24 and Week 52,
 - Proportion of patients with greater than or equal to the minimal clinically important difference (MCID)(≥ 8.9) in SNOT-22 at Week 24,
 - Proportion of patients with overall rhinosinusitis severity VAS ≤ 7 at Week 24,
 - The cumulative distribution function (CDF) of change from baseline in NC, NPS, SNOT-22 and VAS for rhinosinusitis severity at Week 24,
 - Proportion of patients with anosmia by UPSIT scores at Week 24.

2.4.4.4.2 Analyses of other efficacy endpoints for 300 mg q2w versus placebo at Week 24

The change from baseline in VAS for overall rhinosinusitis, NPIF, EQ-5D utility and daily assessed severity of rhinorrhea at Week 24 and percent change from baseline in NC, TSS, daily assessed loss of smell and VAS for overall rhinosinusitis at Week 24, will be assessed for dupilumab 300 mg q2w (pooled A and B arms) versus placebo and will be analyzed using the hybrid method of the WOCF and the MI the same as the primary approach of the co-primary endpoints. Descriptive statistics including number of patients, mean, standard error, and least squares (LS) means will be provided. In addition, difference in LS means and the corresponding 95% confidence intervals (CI) will be provided along with the p-values.

For responder type endpoints including

- The proportion of responders at Week 24 (defined as patients with improvement by at least 1 point in NPS)
- Proportion of responders at Week 24 (defined as patients with improvement by at least 2 points in NPS)
- The proportion of patients with improvement by at least 1 point in NPS and 0.5 reductions in NC at Week 24
- The proportion of patients with MCID \geq 8.9 in SNOT-22 at Week 24
- The proportion of patients with VAS \leq 7 at Week 24,

the Cochran-Mantel-Haenszel test will be performed on the association between the responder status and treatment group, stratified by asthma/NERD status, prior surgery history, and region. Comparisons of the proportions of responders between dupilumab 300mg q2w and placebo will be derived. And corresponding odds ratios and 95% CI will be reported. Patients who are indicated for surgery for NP or receive SCS for any reason will be considered as non-responders for time points after using SCS or surgery. For patients who discontinue treatment without using SCS or surgery, data collected during the off- treatment period will be used to determine the responder/non- responder status. Missing data at Week 24 will be considered as non-responders.

In addition, the cumulative distribution function (CDF) of change from baseline in NC, NPS, SNOT-22 and VAS for rhinosinusitis severity at Week 24 will also be presented by treatment.

2.4.4.4.3 Analyses of efficacy endpoints for Arm A versus placebo at Week 52

The change from baseline in LMK, TSS, UPSIT, daily assessed loss of smell, VAS for overall rhinosinusitis, EQ-5D utility and daily assessed severity of rhinorrhea at Week 52 and percent change from baseline in NC, TSS, daily assessed loss of smell and VAS for overall rhinosinusitis at Week 52 will be assessed separately for dupilumab 300 mg q2w (Arm A) versus placebo and will be analyzed using the hybrid method of the WOCF and the MI in the same fashion as for the key secondary endpoints of change from baseline in NC, in NPS and SNOT-22 at Week 52. Descriptive statistics including number of patients, mean, standard error, and least squares (LS) means will be provided. In addition, difference in LS means and the corresponding 95% confidence intervals (CI) will be provided along with the p-values.

For responder type endpoints including

- The proportion of patients with improvement by at least 1 point in NPS and 0.5 reductions in NC at Week 52

The Cochran-Mantel-Haenszel test will be performed on the association between the responder status and treatment group, stratified by asthma/NERD status, prior surgery history, and region. Comparisons of the proportions of responders between dupilumab 300mg q2w (Arm A) and placebo will be derived. And corresponding odds ratios and 95% CI will be reported. Patients who are indicated for surgery for NP or receive SCS for any reason will be considered as non-responders for time points after using SCS or surgery. For patients who discontinue treatment without using SCS or surgery, data collected during the off-treatment period will be used to determine the responder/non-responder status. Missing data at Week 52 will be considered as non-responders.

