## 7 SELECTION OF PATIENTS

### 7.1 INCLUSION CRITERIA

Patients with bilateral sino-nasal polyposis that despite prior treatment with SCS anytime within the past 2 years; and/or have a medical contraindication/intolerance to SCS; and/or had prior surgery for NP at the screening visit have:

- I 01. An endoscopic bilateral NPS at V1 of at least 5 out of a maximum score of 8 (with a minimum score of 2 in each nasal cavity).
- I 02. Ongoing symptoms (for at least 8 weeks before V1) of:
- Nasal congestion/ blockade/obstruction with moderate or severe (symptom severity score 2 or 3) at V1 and a weekly average severity of greater than 1 at time of randomization (V2).
- AND
- Another symptom such as loss of smell, rhinorrhea (anterior/posterior).
- I 03. Signed written informed consent.

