### 10.1.1 Visit 1 (Week -4/Day -28 ±3 days): Run-in period

Following a discussion of participation in the clinical trial, signed informed consent must be obtained and documented.

The following procedures will then be performed:

- Call IVRS/IWRS to assign patient number, register V1, and obtain first NIMP (NASONEX) box(es).
- Interview to collect patient demographic information, NP information, other medical history (including asthma history, hypersensitivity to aspirin or NSAIDs, NERD, allergy/atopy history, surgical history (including number, type and dates of previous surgery for nasal polyps in the past), and prior and concomitant medications (including background therapy for NP and asthma), courses of SCS in the previous 2 years (number of SCS courses, route of administration doses and duration in the previous 2 years will be entered in the e-CRF), long term antibiotics use [ $>2$  weeks] in the previous year will be also entered in the e-CRF); inform if patient is considered eligible for nasal polyp surgery at study entry.
- Review entry criteria to assess eligibility, with special attention to verify and document the following:
  - Use of SCS for NP within 2 years prior to V1; and/or contraindication/intolerance to SCS; and or prior surgery for NP (whenever in the past),
  - Nasal polyps score of 5 or greater (and at least 2 in each side),
  - Presence of nasal congestion (blockade/obstruction) severity  $\geq 2$  on V1 and loss or reduction of smell and/or rhinorrhea/nasal discharge (anterior/posterior nasal drip),
  - Patients have not received any of the prohibited medications described in [E 03](#) and/or [Section 8.8.1](#).
- Measure vital signs: blood pressure, heart rate, respiration rate, body temperature, weight, height.
- Perform physical examination.
- Perform CT scan (within the time period between V1 and V2, prior to first administration of IMP). In countries for which a specific approval procedure for the CT scan is required by a different committee than the local EC/IRB, patients may be enrolled using a CT available in the previous year or perform an MRI of the sinuses between V1 and V2.
- Perform urine sampling for biomarkers and creatinine.

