2.4.4.4 Time course profile of the efficacy endpoints over 24 and 52 weeks

For the continuous efficacy endpoints, descriptive statistics including number of patients, mean, standard error, and least squares (LS) means will be provided and plotted separately for 300mg q2w (pooled Arms A and B) versus placebo (up to Week 24) and by treatment group (up to Week 52) at each visit during the treatment period. In addition, using the hybrid method of the worst-observation carried forward (WOCF) and the multiple imputation separately at each visit, difference in LS means and the corresponding 95% confidence intervals (CI) will be provided along with the p-values. Such analyses will be conducted on the following variables:

- Change from baseline in NPS
- Change and percent change from baseline in NC
- Change from baseline in CT LMK scores
- Change and percent change from baseline in TSS
- Change from baseline in UPSIT
- Change and percent change from baseline in loss of smell
- Change from baseline in SNOT-22
- For proportion type efficacy endpoints, the response rate at each visit during the treatment period will be summarized and plotted by treatment groups. The odds ratio and the corresponding 95% CI will be derived by tests between dupilumab 300mg q2w and placebo and between dupilumab 300 mg q2w/q4w and placebo, separately at each visit. Patients who are indicated for surgery for NP or receive SCS for any reason will be considered as non-responders for time points after using SCS or surgery. For patients who discontinue treatment without using SCS or surgery, data collected during the off-treatment period will be used to determine the responder/non-responder status. Missing data will be considered as non-responders. Such analyses will be conducted on the following variables:

- Proportion of responders (defined as patients with improvement by at least 1 point in NPS),
- Proportion of responders (defined as patients with improvement by at least 2 point in NPS),
- Proportion of patients with improvement by at least 1 point in NPS and 0.5 reductions in NC
- Proportion of patients with $MCID \geq 8.9$ in SNOT-22
- Proportion of patients with $VAS \leq 7$

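### Patient-level percent change in daily loss of smell can be undefined or extreme, because entry sets no minimum smell score and the SAP has no rule for a zero or very low baseline

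*SAP*

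**What the plan says.** SAP 2.4.4.4.1 lists percent change from baseline at Weeks 24 and 52, with time courses, for nasal congestion (NC), daily loss of smell and TSS. It lists percent change in the rhinosinusitis VAS at Weeks 24 and 52 only.

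SAP 2.4.4.4.2 says the Week 24 measures, among them "percent change from baseline in NC, TSS, daily assessed loss of smell and VAS for overall rhinosinusitis at Week 24", "will be analyzed using the hybrid method of the WOCF and the MI the same as the primary approach of the co-primary endpoints", and that "Descriptive statistics including number of patients, mean, standard error, and least squares (LS) means will be provided", together with differences in LS means, 95% intervals and p-values. SAP 2.4.4.4.3 (Arm A) and 2.4.4.5.1 (Arm B, exploratory) repeat this at Week 52 for "percent change from baseline in NC, TSS, daily assessed loss of smell and VAS for overall rhinosinusitis". The time-course section includes "Change and percent change from baseline in loss of smell" at each visit. SAP 2.4.4 defines the efficacy population as all randomized patients.

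On entry, Protocol 7.1 sets a floor for NC only: "a weekly average severity of greater than 1 at time of randomization (V2"). The second symptom is described as "Another symptom such as loss of smell, rhinorrhea (anterior/posterior"), without a minimum score. The Visit 1 checklist in Protocol 10.1.1 reads "loss or reduction of smell and/or rhinorrhea/nasal discharge (anterior/posterior nasal drip"), so smell loss is not mandatory. No entry criterion uses the VAS.

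SAP 2.4.4.6 and 2.5.1 to 2.5.4 give no formula for percent change and no rule for a zero or very small baseline.

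**The concern.** A percent change is usable as a patient-level outcome only if every baseline is clearly above zero. NC meets that condition through its entry floor, and TSS meets it because NC is one of its components. Loss of smell does not. A patient who qualifies on rhinorrhea may have a smell baseline of 0, where the ratio does not exist, or a small fraction, where ordinary day-to-day variation becomes a change of several hundred percent.

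The planned summaries are means and LS means, which are sensitive to such values, and the scale is lopsided: improvement cannot go below -100%, while worsening is almost unbounded. It is also unclear what happens to a patient with baseline 0. If the sample code in SAP 2.4.4.1 is reused with percent change in place of change, a non-rescued patient's undefined value would look like a missing value and be imputed. A rescued patient would have nothing to carry forward and would drop out of the model. At stake is whether the reported means, intervals and p-values describe all randomized patients, and whether a few patients with almost no smell loss determine them.

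**Working it through.** The plan states no figure for percent change, so there is none to reproduce.

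**Inputs from the documents.** Smell scale 0 to 3 (SAP 2.1.3.2.1.4). Baseline is the mean of 4 to 7 daily integer scores in the 7 days before randomization, otherwise of the most recent 4 (SAP 2.1.3.1). Follow-up is a 4-week mean. Sizes are 240 pooled dupilumab and 120 placebo (SAP 1.3). TSS range 0 to 9; VAS range 0 to 10.

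**Formula.** Percent change = 100 × (follow-up − baseline) / baseline.

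**1. Loss of smell.**
- Baseline 0: division by zero.
- Smallest non-zero baseline (one day scored 1 out of seven): 1/7 = 0.143.
- Follow-up 1: 100 × (1 − 1/7)/(1/7) = +600%.
- Follow-up 3: 100 × (3 − 1/7)/(1/7) = +2000%.
- With only four readings the smallest is 1/4; follow-up 3 then gives +1100%.
- For contrast, a fall from 3 to 1 is −67%.

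**2. NC and TSS for comparison.** With seven readings, the lowest NC average above 1 is 8/7. The largest NC value is 100 × (3 − 8/7)/(8/7) = +162.5%, and the largest TSS value is 100 × (9 − 8/7)/(8/7) = +687.5%. Neither can be undefined.

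**3. VAS.** Baseline 0 is undefined. An assumed baseline of 0.5 gives at most 100 × (10 − 0.5)/0.5 = +1900%.

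**4. Leverage of one patient**, relative to the same patient showing no change.
- +600%: 600/120 = 5.0 points in placebo; 600/240 = 2.5 in the pooled arms.
- +2000%: 16.7 and 8.3 points.
- The SE of the arm difference is SD × √(1/120 + 1/240): 3.4, 4.5 or 6.7 points for assumed SDs of 30, 40 or 60. One such patient can therefore shift the estimate by an amount comparable with its SE.

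**5. Simulation, on assumptions that the documents do not supply.** 240 versus 120 patients; most baselines spread over 1.5 to 3; a 0.5-point drug effect, no placebo change, SD 0.8, scores limited to 0 to 3; near-zero baselines of 0, 1/7, 2/7 or 3/7 in 2, 5 or 10% of patients; zero baselines dropped; unadjusted t-tests. With no near-zero baselines, the SD of percent change is 34 and power exceeds 99%.

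| Effect in near-zero patients | SD in near-zero patients | Power at 2% | at 5% | at 10% |
|---|---|---|---|---|
| 0 | 0.8 | 92% | 79% | 54% |
| 0.5 | 0.8 | 99% | 95% | 93% |
| 0 | 0.4 | 99% | 96% | 86% |
| 0.5 | 0.4 | >99% | >99% | >99% |

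Repeat runs differ by a few points. The SD of percent change rises to 46, 61 and 81 in the first row and to about 43, 52 and 66 in the second. The smallest rise is to 36 (last row, 2%). About 2, 4 to 5, and 9 patients have a zero baseline. Power for absolute change stays above 99% in every setting.

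**The case against.** The strongest reply is that little depends on these analyses. Percent change lies outside the testing hierarchy in SAP 2.4.4.3, and the Arm B version is exploratory. Absolute change in loss of smell is a hierarchy-tested endpoint at Week 24 and is also analysed at Week 52. Absolute VAS change is planned at both times. All of this stands and limits the consequence.

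Second, a reader might infer that some patients definitely have undefined values, or that outliers will dominate the result. The documents give no baseline distribution, so neither can be said. Nor do they support a single power figure. The large losses appear only if near-zero patients get no drug effect yet keep an SD of 0.8, a demanding choice when scores cannot fall below 0. The t-tests also simplify the planned model.

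Third, a reader might infer that the VAS is equally exposed. It is not: patients need NC of 2 or 3 at Visit 1, a weekly NC average above 1 at randomization and a polyp score of at least 5, so a troublesomeness rating near 0 is permitted but implausible. There is also no percent-change time course for the VAS.

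Fourth, TSS can reach +687.5%, so large ratios are not unique to smell. That is correct, but the TSS denominator always exceeds 1, and its extreme needs a patient with almost no smell loss or rhinorrhea, contrary to the spirit of the second-symptom criterion.

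Finally, the number of patients is to be reported for each analysis, so exclusions would not be wholly invisible. A count alone does not say why patients are absent, or whether undefined values were imputed.

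**Conclusion.** The point holds for loss of smell as a defect in what the design allows: the plan specifies a patient-level ratio for all randomized patients, the entry criteria permit a zero or near-zero denominator, and no rule says what then happens. Without a rule, the handling would have to be chosen during programming or after the data are seen.

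The exact results are the undefined value at baseline 0, +600% and +2000% from a baseline of 1/7, and a shift of 5.0 (placebo) or 2.5 (pooled dupilumab) points from one +600% patient. The number of patients affected is unknown. Under an assumed 2 to 10% of near-zero baselines, variance inflation appears in every setting tried (SD from 34 to between 36 and 81), while the power loss ranges from negligible to nearly half, depending on the effect and SD assumed in those patients. For the VAS the gap is real on paper but unlikely to matter. No co-primary or hierarchy-tested conclusion is at risk. The point is worth correcting because the correction is cheap, not because the trial's main inference depends on it.

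**What to change.** For loss of smell, and for consistency the rhinosinusitis VAS, replace the patient-level percent-change ANCOVA in SAP 2.4.4.4.1 to 2.4.4.4.3, 2.4.4.5.1 and (smell only) the time-course section. Report instead the already planned LS mean absolute change per arm, and the difference with its 95% interval, each divided by the overall mean baseline of the ITT population and multiplied by 100. Every randomized patient then stays in, and a percentage is still available. Patient-level percent change can remain for NC and TSS.

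If patient-level percent change in smell or VAS is kept, make it descriptive (median and quartiles), state the formula, exclude zero baselines by a stated rule, and report the number excluded per arm.

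The cost is SAP wording and minor programming. The separate p-value for individual percent change is lost for these other-secondary and exploratory measures. The protocol's efficacy sections do not list percent change in these scores, so nothing there has to change.

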2.4.4.4 Time course profile of the efficacy endpoints over 24 and 52 weeks

For the continuous efficacy endpoints, descriptive statistics including number of patients, mean, standard error, and least squares (LS) means will be provided and plotted separately for 300mg q2w (pooled Arms A and B) versus placebo (up to Week 24) and by treatment group (up to Week 52) at each visit during the treatment period. In addition, using the hybrid method of the worst-observation carried forward (WOCF) and the multiple imputation separately at each visit, difference in LS means and the corresponding 95% confidence intervals (CI) will be provided along with the p-values. Such analyses will be conducted on the following variables:

- Change from baseline in NPS
- Change and percent change from baseline in NC
- Change from baseline in CT LMK scores
- Change and percent change from baseline in TSS
- Change from baseline in UPSIT
- Change and percent change from baseline in loss of smell
- Change from baseline in SNOT-22
- For proportion type efficacy endpoints, the response rate at each visit during the treatment period will be summarized and plotted by treatment groups. The odds ratio and the corresponding 95% CI will be derived by tests between dupilumab 300mg q2w and placebo and between dupilumab 300 mg q2w/q4w and placebo, separately at each visit. Patients who are indicated for surgery for NP or receive SCS for any reason will be considered as non-responders for time points after using SCS or surgery. For patients who discontinue treatment without using SCS or surgery, data collected during the off-treatment period will be used to determine the responder/non-responder status. Missing data will be considered as non-responders. Such analyses will be conducted on the following variables:

- Proportion of responders (defined as patients with improvement by at least 1 point in NPS),
- Proportion of responders (defined as patients with improvement by at least 2 point in NPS),
- Proportion of patients with improvement by at least 1 point in NPS and 0.5 reductions in NC
- Proportion of patients with $MCID \geq 8.9$ in SNOT-22
- Proportion of patients with $VAS \leq 7$

